4.4. Re-screening

Subjects who are screened but ultimately discontinued prior to receipt of PF-06939926 for reasons other than a confirmed, non-transient failure to meet all eligibility criteria (eg, enrollment pause due to regulatory or safety review, operational issues causing significant delays, etc) may be allowed to re-screen during the study while enrollment remains open. In this case, the subject number assigned at the initial screening will be documented as a screen failure the subject would be issued a new subject number for the

re-screen. Re-screened subjects will re-consent, and screening assessments will need to be repeated, as described in Section 6.1.

4.5. Lifestyle Requirements

4.5.1. Activity

Subjects should be instructed to continue with routine physical therapy including stretching or use of orthoses to prevent or minimize contractures or muscle deformities.

Subjects will be instructed to maintain normal activity levels and avoid activities that are not part of their normal daily routine within 24 hours of study visits where imaging or functional assessments will be performed.

As this study involves a viral vector, it is suggested that subjects and those around them be reminded to practice good general hygiene for the first 1-2 months after receiving PF-06939926, such as the following: (1) thoroughly washing hands with soap after using the bathroom, before preparing or touching food, or after blowing one's nose, coughing, sneezing, etc.; (2) avoiding contact with persons who might be sick; and (3) not sharing glasses, dishes, or utensils with other individuals.

In addition, for the first month following administration of PF-06939926, it is suggested that the caregivers assist the subjects with monitoring fluid intake and output. Specifically, the recommendations are that subjects consume at least 1 liter of water per day and pass urine at least 3 times during each 24-hour period through the first month, or longer if deemed clinically necessary. If fluid intake and output are observed to be less than these thresholds, then subjects (and/or caregivers) should be instructed to promptly contact the site for a possible unscheduled visit and/or biospecimen collection.

4.5.2. Contraception

All subjects who are, in the opinion of the investigator, able to father children and sexually active and at risk for pregnancy with their partner(s) must agree to use a highly effective method of contraception consistently and correctly for the duration of the study, including long-term follow-up. The investigator or his or her designee, in consultation with the subject and/or the subject's legal caregiver (depending on the subject's age and appropriateness of this sensitive topic), will confirm that the subject has selected an appropriate method of contraception for the individual and partner from the permitted list of contraception methods (see below) and will confirm that the subject has been instructed in its consistent and correct use. Throughout the study, the investigator or designee will inform the subject and/or legal caregiver of the need to use highly effective contraception consistently and correctly and document the conversation and the subject's affirmation in the subject's chart (subjects need to affirm their consistent and correct use of at least 1 of the selected methods of contraception). In addition, the investigator or designee will instruct the subject and/or legal caregiver to call immediately if the selected contraception method is discontinued or if pregnancy is known or suspected.

Highly effective methods of contraception are those that, alone or in combination, result in a failure rate of less than 1% per year when used consistently and correctly (ie, perfect use) and include the following:

- 1. Male condom used WITH a separate spermicide product (ie, foam, gel, film, cream, or suppository);
- 2. Male sterilization with absence of sperm in the post-vasectomy ejaculate.

NOTE: Sexual abstinence, defined as completely and persistently refraining from all heterosexual intercourse (including during the entire period of risk associated with the study treatments) may obviate the need for contraception ONLY if this is the preferred and usual lifestyle of the subject.

4.6. Sponsor's Qualified Medical Personnel

The contact information for the sponsor's appropriately qualified medical personnel for the study is documented in the study contact list located in the supporting sponsor study team electronic storage site and/or study portal.

To facilitate access to appropriately qualified medical personnel on study-related medical questions or problems, subjects are provided with a contact card. The contact card contains, at a minimum, protocol and investigational product identifiers, subject study numbers, contact information for the investigator site, and contact details for a contact center in the event that the investigator site staff cannot be reached to provide advice on a medical question or problem originating from another healthcare professional not involved in the subject's participation in the study. The contact number can also be used by investigator staff if they are seeking advice on medical questions or problems; however, it should be used only in the event that the established communication pathways between the investigator site and the sponsor study team are not available. It is therefore intended to augment, but not replace, the established communication pathways between the investigator site and the sponsor study team for advice on medical questions or problems that may arise during the study. The contact number is not intended for use by the subject directly, and if a subject calls that number, he or she will be directed back to the investigator site.

5. STUDY TREATMENTS

For the purposes of this study, and per International Conference on Harmonisation (ICH) guidelines, investigational product is defined as a pharmaceutical form of an active ingredient or placebo being tested or used as a reference/comparator in a clinical trial, including a product with a marketing authorization when used or assembled (formulated or packaged) in a way different from the approved form, or when used for an unapproved indication, or when used to gain further information about an approved use (ICH E6 1.33).

For this study, the investigational product is PF-06939926.

Refer to the Investigational Product Manual and the Administration Card for details regarding the preparation and administration of this investigational product.

Subjects will be treated with a single IV infusion of PF-06939926. Please refer to Investigational Product Manual for complete information on storage, stability, preparation and administration of PF-06939926.

This study is an open-label, non-randomized study in which subjects will receive a single IV infusion of an ascending dose of PF-06939926. Subjects in the low-dose cohort will receive a single infusion containing 1E+14 vg/kg, and subjects in the high-dose cohort are planned to receive a single infusion containing 3E+14 vg/kg per ITR-based titer method. However, should a dose-limiting safety event occur at this highest dose level, subsequent subjects may be administered 2E+14 vg/kg or lower per ITR-based titer method. The dose will be calculated based on the subject weight, which will be obtained at the Baseline visit (see Section 5.3.1).

To mitigate risk of an immune response and drug-induced liver injury, as described in Section 1.5, subjects will temporarily replace their daily glucocorticoid regimen as follows:

- 1. Between 1 and 4 hours prior to infusion of PF-06939926: receipt of single dose of IV methylprednisolone ≥2 mg/kg;
- 2. For first 2 weeks post-infusion of PF-06939926: switch of daily glucocorticoid dose to ≥2 mg/kg/day of oral prednisone or prednisolone;
- 3. For Weeks 3 and 4 post-infusion of PF-06939926: reduction of daily glucocorticoid dose to ≥1.5 mg/kg/day of oral prednisone or prednisolone;
- 4. For Weeks 5, 6, 7, and 8 post-infusion: reduction of oral prednisone or prednisolone dose to a minimum of ≥1.0 mg/kg/day;
- 5. For Weeks 9, 10, 11, and 12 post-infusion: reduction of oral prednisone or prednisolone dose to a minimum of 0.75 mg/kg/day;
- 6. After Week 12 post-infusion: reduction of oral prednisone or prednisolone dose to a minimum of 0.5 mg/kg/day or return to pre-study daily doses of prednisone or prednisolone, whichever dose is higher.

These doses will be calculated within approximately 10% of the subject's body weight. Provided that no signals of a latent immune response are present following these 3 months of descending dose levels of prednisone or prednisolone, subjects may then return to their pre-study dose levels of daily glucocorticoids (eg, prednisone, prednisolone, or deflazacort) for at least the remainder of the first year following receipt of PF-06939926.

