6.4. Visit 4 (Week 2): Day 14 ± 1 Day

Assessments to be performed at this visit include:

- Brief physical and neurological examination;
- Vital signs: Blood pressure, pulse rate, respiratory rate, and body temperature;
- Triplicate 12-lead ECG;
- Clinical laboratory assessment:
 - *Blood sample:*
 - Clinical safety (Table 1), including CCl but excluding CK-MB;

CC

[figure not shown]
- Ouestionnaires: *C-SSRS*:
 - FOR ALL SUBJECTS WHO WERE ≤ 12 YEARS OLD AT SCREENING: Children's Since Last Visit (Version 6/23/10).
 - FOR ALL SUBJECTS WHO WERE AGED >12 YEARS OLD AT SCREENING: Since Last Visit (Version 1/14/09).

- **AE monitoring**, including infusion site reaction monitoring;
- Concomitant medication monitoring;
 - Oral prednisone or prednisolone: Subjects will taper the oral prednisone or prednisolone dose to ≥1 mg/kg/day for the remainder of the 1st month post-investigational product administration, or return to their pre-study daily doses of prednisone or prednisolone, whichever is higher. Confirmation of compliance may be collected via a subject dosing diary, but must be specifically discussed and documented during this visit.
- **Fluid intake/output:** review with caregiver that subject has adequate fluid intake and output, as described in Section 4.5.1.

6.5. Remote Visits 5, 7, 9, 11.1, 11.2, 11.3, 12.1, 12.2 (Weeks 3, 6, 10, 15, 19, 22, 32, 39): Days 21, 45, 75 ±3 Days, and Days 106, 135, 155, 225, 270 ±7 Days

The assessments at these visits may be performed remotely unless clinical concern or subject preference warrants an in-person visit. In the case of a remote visit, the site will coordinate a local phlebotomist to perform the sample collections at the subject's home.

- Clinical laboratory assessment:
 - *Blood sample:*

- Wellness check-in: Site staff will follow-up by contacting the subject and/or caregiver to discuss any new adverse events and/or changes to concomitant medications, including compliance with daily oral prednisone or prednisolone.
 - Week 3 check-in will also include confirmation of adequate fluid intake and output, as described in Section 4.5.1.
- Activity monitoring (only at Week 39) Activity monitors will be sent to the subject's home to wear continuously for the next 2 weeks in free-living conditions.

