6.6. Visit 6 (Week 4): Day 30 ± 3 Days

Assessments to be performed at this visit include:

- Brief physical and neurological examination;
- Vital signs: Blood pressure, pulse rate, respiratory rate, and body temperature;
- Triplicate 12-lead ECG;
- Clinical laboratory assessment:
 - *Blood sample*:
 - Clinical safety (Table 1), including CCl
 well as re-start collection of CK-MB going forward;
- AE monitoring, including infusion site monitoring;
- Concomitant medication monitoring;
 - Oral prednisone or prednisolone: subjects will taper the oral prednisone or prednisolone dose to a minimum of 0.75 mg/kg/day for 1 month or return to their pre-study daily doses of prednisone or prednisolone, whichever is higher.
 Confirmation of compliance may be collected via a subject dosing diary, but must be specifically discussed and documented during this visit.
- **Fluid intake/output:** review with caregiver that subject has adequate fluid intake and output, as described in Section 4.5.1.

[figure not shown]

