6.7. Visit 8 (Week 8): Day 60 ± 3 Days

The assessments to be performed at this visit include:

- Brief physical and neurological examination.
- Height and Weight;
- **Vital signs:** Blood pressure, pulse rate, respiratory rate, and if clinically indicated, body temperature;
- Triplicate 12-lead ECG;

• Clinical laboratory assessment:

• Blood sample:

- **Muscle biopsies**: if applicable, it will be performed under anesthesia either at this visit or the Week 12 (Day 90) visit, as determined by the sponsor and investigator;
- AE monitoring including infusion site monitoring;
- Concomitant medication monitoring;
 - Oral prednisone or prednisolone: subjects will taper the oral prednisone or
 prednisolone dose to a minimum of 0.5 mg/kg/day for 1 month or return to their
 pre-study daily doses of prednisone or prednisolone, whichever is higher.
 Confirmation of compliance may be collected via a subject dosing diary, but must be
 specifically discussed and documented during this visit.

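### Protocol Sections 6.4, 6.6 and 6.7 give different minimum steroid doses for Weeks 3-12 from Section 5, lower for some subjects and higher for others

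*Protocol*

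**What the plan says.** Section 5 of the protocol (Study Treatments) replaces each subject's daily glucocorticoid with a stepped regimen after infusion. After two weeks at 2 mg/kg/day or more, the steps are:

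- Item 3: "For Weeks 3 and 4 post-infusion of PF-06939926: reduction of daily glucocorticoid dose to ≥1.5 mg/kg/day of oral prednisone or prednisolone"
- Item 4: "For Weeks 5, 6, 7, and 8 post-infusion: reduction of oral prednisone or prednisolone dose to a minimum of ≥1.0 mg/kg/day"
- Item 5: "For Weeks 9, 10, 11, and 12 post-infusion: reduction of oral prednisone or prednisolone dose to a minimum of 0.75 mg/kg/day"

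The visit sections give the taper again with other numbers:

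- Section 6.4 (Day 14): "Subjects will taper the oral prednisone or prednisolone dose to ≥1 mg/kg/day for the remainder of the 1st month"
- Section 6.6 (Day 30): "dose to a minimum of 0.75 mg/kg/day for 1 month"
- Section 6.7 (Day 60): "dose to a minimum of 0.5 mg/kg/day for 1 month"

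Each visit instruction adds an alternative, in Section 6.4 worded "or return to their pre-study daily doses of prednisone or prednisolone, whichever is higher". Section 5 has a higher-of rule only in item 6, after Week 12. Each of the three visit sections also says that taper compliance "must be specifically discussed and documented during this visit".

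Both sets are current operative text. Section 5 lets doses be calculated to within about 10% of body weight. Eligibility (Section 4.1) requires a stable pre-study dose of at least 0.25 mg/kg/day and sets no maximum.

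**The concern.** A site that doses from the visit text and a site that doses from Section 5 can give the same subject different amounts of steroid, and each can believe that it follows the protocol. Section 5 gives the regimen's purpose as reducing the risk of an immune response and of drug-induced liver injury. The Amendment 7 log entry gives adrenal insufficiency as a reason for the slower taper.

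The analysis consequence is narrower. SAP 4.2 requires all protocol deviations to be compiled and graded major or minor before database closure. A dose between the two minima is compliant under one section and a deviation under the other.

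**Working it through.** **Inputs.** Section 5 minima are 1.5, 1.0 and 0.75 mg/kg/day for Weeks 3-4, 5-8 and 9-12 (14, 28 and 28 days). Visit-text minima are 1.0, 0.75 and 0.5 mg/kg/day, or the pre-study prednisone/prednisolone dose p if higher. The documents do not give the distribution of p, so a range is shown. The plan states no cumulative figure to reproduce.

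**Section 5 total, Weeks 3-12.** 1.5×14 + 1.0×28 + 0.75×28 = 21 + 28 + 21 = 70 mg/kg.

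**Visit-text total on the same week boundaries.** max(1.0, p)×14 + max(0.75, p)×28 + max(0.5, p)×28.

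| p (mg/kg/day) | Weeks 3-4 (Section 5: 1.5) | Weeks 5-8 (Section 5: 1.0) | Weeks 9-12 (Section 5: 0.75) | Total (mg/kg) | Against 70 |
|---|---|---|---|---|---|
| 0.5 or less | 1.0 | 0.75 | 0.5 | 49 | −21 (30%) |
| 0.6 | 1.0 | 0.75 | 0.6 | 51.8 | −18.2 (26%) |
| 0.75 | 1.0 | 0.75 | 0.75 | 56 | −14 (20%) |
| 1.0 | 1.0 | 1.0 | 1.0 | 70 | 0 |
| 1.25 | 1.25 | 1.25 | 1.25 | 87.5 | +17.5 |
| 1.5 | 1.5 | 1.5 | 1.5 | 105 | +35 |

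**Low pre-study dose.** At p of 0.5 or less, the shortfalls by period are 0.5/1.5 = 33%, 0.25/1.0 = 25% and 0.25/0.75 = 33%.

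**Sensitivity to the switch days.** The visit text changes dose at Days 14, 30 and 60, not at the Section 5 week boundaries. At nominal days, Days 15-84 give 1.0×16 + 0.75×30 + 0.5×24 = 16 + 22.5 + 12 = 50.5 mg/kg. The gap is then 19.5 mg/kg (28%).

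**High pre-study dose.** Above p = 0.75 the visit minimum exceeds Section 5 in Weeks 9-12, and above 1.0 it does so in Weeks 5-8 as well.

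- At p = 1.0 the totals agree, but only because Weeks 3-4 are 0.5×14 = 7 mg/kg lower and Weeks 9-12 are 0.25×28 = 7 mg/kg higher.
- At p = 1.25, Weeks 3-4 are 0.25×14 = 3.5 mg/kg lower. Weeks 5-12 are 1.25×56 = 70 against 28 + 21 = 49, which is 21 mg/kg higher.

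**The 10% allowance.** For a subject at p of 0.5 or less, 90% of the Section 5 minima is 1.35, 0.90 and 0.675. Each is still above 110% of the visit minima (1.10, 0.825 and 0.55), so the allowance closes none of the three gaps.

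**Where the mismatch seems to come from.** In protocol Appendix 3, the Amendment 5 entry that introduced the 1 mg/kg/day step lists Section 6.4 among the sections changed. The Amendment 7 entry for the slower taper (3 June 2021) names Section 5 only.

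**Are tapers still running?** The rationale for SAP version 5 (11 May 2022) says the study will enrol no more subjects. Schedule of Activities footnote g puts dosing up to 28 days after Baseline: 11 May + 28 days = 8 June 2022, and + 84 days = 31 August 2022. That is 57 days before the current SAP (27 October 2022).

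**The case against.** The best reply is that Section 5 plainly governs. Schedule of Activities footnote s, Sections 5.7.1 and 5.8 and Appendix 1 all send the reader there for this regimen. Both texts are minima, so giving the larger of the two satisfies both. Sections 1.5.1 and 5.8 allow more steroid if liver markers rise or an immune reaction occurs. This stands as evidence of intent, and it shows that sites were not asked for the impossible. It does not remove the contradiction: there is no precedence clause, the opening of the Schedule of Activities sends sites to the visit procedures for detail, and compliance is documented at those visits.

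Appendix 1 contains the lower 1.0, 0.75 and 0.5 steps, but only as a possible change for the sirolimus cohort, pending data review and at the sponsor's discretion. It does not explain the visit text for other subjects.

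A reader might infer three stronger claims that the documents do not support:

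- **The visit text is always the lower standard.** This fails above a pre-study dose of 0.75 mg/kg/day, as the table shows.
- **The number affected can be bounded from the cohort sizes in SAP 2.5.** Dosing by protocol version is not reported, and the visit text of Amendments 7 and 8 is not shown. The high-dose cohort mixes both titer labels, and the one sirolimus participant may have been moved to the Appendix 1 regimen.
- **The lower taper caused harm or biases a result.** No harm from it is shown. The SAP defines no per-protocol set, the secondary estimand (SAP 2.3) applies whatever the glucocorticoid adherence, and actual use is listed under SAP 6.5.2 in any case.

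**Conclusion.** The point holds as an internal contradiction in a safety regimen, and it is minor. It runs in both directions, and its size depends on the pre-study dose. The largest shortfall of the visit text against Section 5 is 28% to 30% of the Weeks 3-12 minimum, at a pre-study dose of 0.5 mg/kg/day or less. Only at 1.5 mg/kg/day or more does the visit text fall short in no period.

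Two things are inference: that the visit doses were left behind when Amendment 7 slowed the taper, and that all tapers had ended by the current SAP. If the second is right, what remains to be gained is correct deviation classification. No planned estimate changes.

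**What to change.** In the protocol:

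- In Sections 6.4, 6.6 and 6.7, replace the doses with 1.5, 1.0 and 0.75 mg/kg/day, and keep the rule that a higher pre-study prednisone or prednisolone dose applies.
- Add the same higher-of rule to Section 5 items 3 to 5. A bare cross-reference to Section 5 would delete that rule and, at a pre-study dose of 1.25 mg/kg/day, cut the Weeks 5-12 minimum from 70 to 49 mg/kg.
- Align Section 6.8, which returns subjects to the pre-study dose at Week 12, with Section 5 item 6 (a 0.5 mg/kg/day minimum) and the condition in the paragraph after it.
- Refer to Appendix 1 where the sponsor has approved that regimen.

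In the SAP 4.2 deviation review, judge each subject against the Section 5 regimen of the protocol version in force at his dosing, with the higher-of rule where that version states it. The current Section 5 should not be applied to subjects dosed under earlier versions.

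The cost is wording in four visit sections and three items of Section 5, plus one rule in the deviation review. It needs no new procedures, data or subjects.

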5.1. Allocation to Treatment

The investigator's knowledge of the treatment should not influence the decision to enroll a particular subject or affect the order in which subjects are enrolled.

Allocation of subjects for treatment will be performed by the sponsor's study management team. An interactive response technology (IRT) system (interactive Web-based response [IRT] will be used for subject screening and enrollment. The site personnel (study coordinator or specified designee) will be required to enter or select information including but not limited to the user's identification (ID) and password, the protocol number, and the subject-specific identification number (SSID), the subject's weight collected at Baseline (Section 5.3.1) and subject's date of birth. The site personnel will then be provided with an enrollment number via the IRT system. The IRT system will provide a confirmation report containing the subject number, and enrollment number. The confirmation report must be retained by the dispenser in the site files.

Subjects will be allocated to the open dose cohort according to their enrollment number. Once subject screening and enrollment numbers have been assigned, they cannot be reassigned.

The study-specific IRT reference manual will provide the contact information and further details on the use of the IRT system.

5.2. Subject Compliance

Investigational product will be administered by the appropriately designated study staff at the investigator site.

5.3. Investigational Product Supplies

5.3.1. Dosage Form(s) and Packaging

The amount of study drug shipped to site will be based on subject's Baseline body weight and the lot-specific concentration of PF-06939926. A shipment order will be raised once the subject is registered (ie, enrolled) following confirmation of eligibility. Thus, it is highly recommended that all subject-level details, especially body weight, are confirmed by two (2) site personnel prior to enrolling the subject, so as to ensure that the appropriate amount of study drug is sent to the site for dosing. Guidance for collecting the most accurate weight is provided in Section 7.2.4.2. As a minimum of 2 weeks (14 calendar days) is required for shipment of study drug, enrollment should occur promptly following the measurement of the subject's weight at Baseline.

The dose will be prepared by the site pharmacist following the instructions in the Investigational Product Manual.

PF-06939926 will be supplied as a sterile, frozen solution requiring thawing and further dilution for IV administration. The drug product is supplied in a clear closed vial configuration with stopper and a cap in place. Each vial contains a 5 mL nominal fill volume of PF-06939926. Each lot of PF-06939926 will have a lot-specific titer concentration.

Details of the drug product packaging, accompanying shipment documentation and drug product preparation are provided in the Investigational Product Manual.

All ancillary supplies used to prepare and administer doses will be provided by the clinical site conducting the study unless otherwise agreed by the sponsor.

